4.2.2 Exclusion criteria

Any subject who meets one or more of the following exclusion criteria will not be included in this clinical trial.

- Subject with particular forms of rosacea (rosacea conglobata, rosacea fulminans, isolated pustulosis of the chin, isolated rhinophyma) or other facial dermatoses that may be confounded with papulopustular rosacea, such as perioral dermatitis, facial keratosis pilaris, acute lupus erythematosus, actinic telangiectasia or seborrheic dermatitis and acne vulgaris
- 2. Subject with more than 2 nodules of rosacea (a circumscribed, elevated, solid lesion more than 1.0cm in diameter with palpable depth) on the face
- Subject with known allergies or sensitivities to any components of the formulation of the study drugs being tested (either Ivermectin 1% cream or Doxycycline, see package inserts)
- 4. Female who is lactating.
- 5. Female who intends to conceive a child during the clinical trial during the study period and for at least 4 weeks after the last study drug(s) use.
- 6. Currently participating in any other clinical trial of a drug or device OR participated within 30 days prior to baseline OR is in an exclusion period (if verifiable) from a previous clinical trial.
- 7. The subject has received, applied or taken the following treatments within the specified time frame prior to the Screening/Baseline visit:

Protocol N° RD.03.SPR.113322

version Final dated 10-FEB-2017

Page 34 of 106 CONFIDENTIAL

Topical facial treatments or procedures on the face:		
Astringents or abrasives (scrubs, exfoliating cleansers and products containing salicylic acid or alcohol)	2 days	
Antibiotics (e.g. metronidazole or macrolides)	4 weeks	
Benzoyl Peroxide	4 weeks	
Anti-rosacea drugs (e.g. azelaic acid, brimonidine, oxymetazoline)	4 weeks	
Immunomodulators	4 weeks	
Corticosteroids	4 weeks	
Retinoids	4 weeks	
Any procedure on the face (e.g. laser, intense pulsed light-IPL, facial peel, dermabrasion, electrocoagulation, Thermage®)	6 weeks	
Systemic treatments:	1	
Antibiotics (e.g. cyclines, macrolides, metronidazole)	4 weeks	
Corticosteroids	4 weeks	
Immunomodulators	4 weeks	
Oral Ivermectin	4 weeks	

Protocol N° RD.03.SPR.113322

version Final dated 10-FEB-2017

Page 35 of 106 CONFIDENTIAL

Other drugs used for the treatment of acne or rosacea (eg: spironolactone)	4 weeks
Oral retinoids	12 weeks
Anticoagulants of the dicoumarol type	4 weeks
Sulphonylurea oral antidiabetic agents	1 week
Other treatments:	
Inhaled Corticosteroids (for asthma or chronic obstructive pulmonary disease - COPD)	4 weeks
Oxymetazoline (any route; e.g. eye drops, nasal sprays) or vasodilators	4 weeks

- 8. The subject is unwilling to refrain from use of prohibited medication during the clinical trial (see section 4.3.5)
- 9. Subject who is vulnerable as defined in Section 1.61 of the International Conference on Harmonisation (ICH) Guideline for Good Clinical Practice (GCP); eg: adult subject under guardianship, hospitalized subject in a public or private institution for a reason other than the research, and subject deprived of his/her freedom
- 10. The subject has history of alcohol or drug abuse (positive urine drug screen and/or alcohol test) within the previous 12 months.
- 11. The subject is a study site staff member (investigator, study nurse, etc.) or a relative of one.
- 12. The initiation of a hormonal method of contraception within 1 month of baseline, or discontinuation during the course of study, or change in the actual product within 1 month of baseline or planned during the study
- 13. Subject with clinically significant abnormal laboratory finding at the screening/baseline visit or an underlying known disease, a surgical or medical condition, which in the judgment of the Investigator, would put the subjects at risk (e.g., uncontrolled chronic or serious diseases which would normally prevent participation in any clinical study, such as cancer, leukemia or hematologic dyscrasia), or might confound the study assessments (e.g. other dermatological diseases), or might interfere with the subject's study participation (e.g. planned hospitalization during the study)
- 14. Subject who is at risk in terms of precautions, warnings, and contra-indication (see package insert)

Protocol N° RD.03.SPR.113322

version Final dated 10-FEB-2017

Page 36 of 106 CONFIDENTIAL

- 15. Subject with hairs on the treated area that might interfere with study assessments
- 16. Subject exposed to excessive UV radiation within two weeks prior to the Baseline visit, or subjects planning exposure during the study (e.g. phototherapy, occupational exposure to the sun, planned holidays with excessive sun during the study period, tanning salon)

4.3 PRIOR AND CONCOMITANT THERAPIES

4.3.1 **Definition**

Previous therapies (drugs and/or procedures) are defined as therapies that have been stopped within 6 months prior to the first investigational product application/intake.

An exception will be made on the last rosacea treatment taken, where no limit on period of time will be applied upon data collection.

Concomitant therapies are defined as follows:

- any existing therapies ongoing at the time of the screening/baseline visit, or
- any changes to existing therapies (such as changes in dose or formulation) during the course of the clinical trial, or
- any new therapies received by the subject since the screening/baseline visit

4.3.2 Categories

The following two categories will be considered for previous and concomitant therapies:

- Drugs/therapies including, but not limited to, prescription, over-the-counter (OTC), birth control pills/patches/hormonal devices, vitamins, moisturizers, sunscreens, herbal medicines/supplements, and homeopathic preparations.
- Medical and surgical procedures including, but not limited to, laser/radiation procedures, dermal fillers, X-rays, etc.

4.3.3 **Recording**

Previous and concomitant therapies will be recorded on the Drugs/Therapies Form (for drugs/therapies) and/or on the Medical and Surgical Procedures form (for medical/surgical procedures) in the case report form (CRF).

Concomitant therapies will be recorded, reviewed, and updated at each trial visit.

Protocol N° RD.03.SPR.113322

version Final dated 10-FEB-2017

Page 37 of 106 CONFIDENTIAL

Any new concomitant therapy or modification of an existing therapy may be linked to an adverse event (AE). A corresponding Adverse Event Form must be completed to account for the change in therapy, except in some cases such as therapy used for prophylaxis, dose modification for a chronic condition, etc.

4.3.4 Authorised therapies during the clinical trial.

Unless listed in the exclusion criteria above or in the prohibited therapies (see sections 4.2.2 and 4.3.5), all therapies are authorized.

Subjects must use the study-provided cleanser, moisturizer/sunscreen for skin care as described in section 6.2.

Subjects may use cosmetics and make-up if they are applied after study drug application.

Subjects may not use foundation make-up or study provided moisturizer/sunscreen on the days of the visits.

4.3.5 Prohibited therapies during the clinical trial

The following therapies are prohibited because they may interfere with the efficacy and/or safety assessment of the investigational products, or because they may interact with the metabolism of the investigational products:

- All topical or systemic therapies listed as exclusion criteria (section 4.2.2)
- Chronic use (>14 days) of sulpha drugs, erythromycin, cephalosporin, and quinolones
- Use of systemic tetracycline antibiotics or tetracycline-like (doxycycline) antibiotics in conjunction with penicillin (drug interactions with bacteriostatic and bactericidal effects).
- Use of Rifampicin, barbiturates, carbamazepine, diphenylhydantoin, primidone, phenytoin (hepatic enzyme inducers which will thereby decrease doxycycline's half-life) and cyclosporine.
- The concurrent use of tetracycline and methoxyflurane has been reported to result in fatal renal toxicity
- For ocular rosacea if new therapy required like topical ophthalmic treatments (including antibiotics eye drops or steroids); but can continue if stable over the past 2 weeks and planned to be maintained during the study (authorised to use lubricating ointments, artificial tears, eyelid care during the study).
- Chronic use (>14 consecutive days) of NSAIDs, except chronic use of aspirin at subanalgesic dose (≤ 325mg QD) is permitted for patients requiring platelet aggregation inhibitors (dose modifications on PI discretion, refer SmPC)

Protocol N° RD.03.SPR.113322

version Final dated 10-FEB-2017

Page 38 of 106 CONFIDENTIAL

- Use of protein pump inhibitors
- Any other drugs/procedures which at the investigator's judgement are liable to interfere or interact with the efficacy and the safety of investigational products.

Antacids and vitamins containing aluminum, calcium, or magnesium are allowed only if are taken at least 1.5 hours before or 3 hours after the intake of study medication. A shorter interval is prohibited because these agents might impair drug absorption.

If prohibited therapies become a necessary treatment for the safety or best interest of the subject, *GALDERMA R&D* will be notified to discuss possible alternatives prior to administration of a prohibited therapy and to discuss the pertinence and the modalities for the subject to continue in the clinical trial.

4.4 PROCEDURES / REASONS FOR DISCONTINUATION

An Investigator may decide to discontinue a subject from the clinical trial for safety reasons.

Although the importance of completing the entire clinical trial should be explained to the subject by the clinical trial personnel, any subject is free to discontinue his/her participation in this clinical trial at any time and for whatever reason, specified or unspecified, and without prejudice.

Subjects who discontinue the clinical trial prematurely should be fully evaluated, whenever possible.

The procedures designated for the early termination visit will be completed for all premature discontinuation subjects. The appropriate eCRF pages for the next scheduled visit should be completed.

For all subjects who prematurely discontinue the clinical trial, the reason must be carefully documented by the investigator on the Exit Form, and, if applicable, on the Adverse Event Form for discontinuation due to an AE.

A subject who has been randomized and assigned a kit number cannot be replaced by another subject if he/she discontinues the clinical trial for any reason.

In the case of early termination, the investigator should ensure that the subject receives appropriate therapy for his/her condition.

GALDERMA R&D may also decide to prematurely terminate or suspend the clinical trial or the participation of a subject in the clinical trial.

All data gathered on the subject prior to termination will be made available to GALDERMA R&D.

Protocol N° RD.03.SPR.113322

version Final dated 10-FEB-2017

Page 39 of 106 CONFIDENTIAL

Reasons for clinical trial completion/discontinuation, as listed on the Exit Form of the CRF are described below:

Normal Study Completion	Subject completes the clinical trial as planned in protocol.
Pregnancy	Withdraw the subject from the clinical trial following the procedure described in the protocol section 8.3
Adverse Event	Complete CRF Adverse Event Form.
Withdrawal by subject	Includes consent withdrawal, subject relocation, schedule conflicts, etc Does not include AE Explain the reason for withdrawal in the comments section of the CRF Exit Form.
Protocol Violation	Explain the violation in the comments section of the CRF Exit Form
Lost to Follow-up	Confirm with 2 documented phone calls and a certified letter (delivery receipt requested) without response. Explain in the comments section of the CRF Exit Form.
Other	This category is to be used for a subject who discontinues for a reason other than those specified in the predefined categories above. Explain the reason for discontinuation in the comments section of CRF Exit Form.

If reason for discontinuation is "subject request" or "other", the subject must be questioned to rule out the possibility of an AE; this should be documented in the CRF.

Protocol N° RD.03.SPR.113322

version Final dated 10-FEB-2017

Page 40 of 106 CONFIDENTIAL

5. INVESTIGATIONAL PLAN

5.1 OVERALL CLINICAL TRIAL DESIGN

This clinical trial will be conducted as a multi-center, randomized, investigator-blind, controlled and parallel-group study in subjects with severe rosacea characterized by persistent diffuse facial erythema and inflammatory lesions (papules and pustules), and meeting other specific eligibility criteria.

A total of 270 subjects will be enrolled (ie: 135 in each group) in approximately 50 sites in the USA, Canada and Europe. Approximately 5 subjects are planned from each site.

Subjects will be enrolled at baseline and treated for 12 weeks with either Ivermectin 1% cream associated with Doxycycline 40 mg MR (CD2475-101) capsules or Ivermectin 1% cream associated with CD2475-101 placebo capsules.

There will be two parallel groups, randomized in a ratio of [1:1].

There will be up to 5 trial visits: at baseline, Screening/Baseline, Week 4 (±3 days), Week 8 (±3 days), and Week 12 (±5 days).

5.2 DISCUSSION OF CLINICAL TRIAL DESIGN

IVM 1% cream and oral Doxycycline 40 mg MR have been individually approved for rosacea treatment in US, Canada and Europe, with demonstrated efficacy and good safety profile including in severe rosacea population.

They will be used in this trial in their indication and approved dose and regimen.

Unlike clinical studies evaluating monotherapy approaches, clinicians often use a combination of topical and oral therapy for patients with severe rosacea, as an increased or additive benefit has been suggested with combination regimens.

Topical Ivermectin cream (10 mg/g) and systemic, oral Doxycycline 40 mg MR (modified-release) have only been evaluated individually so far, but never as an association. The combined therapeutic approach of both drugs association may be more beneficial, but has never been assessed for rosacea treatment in a randomized clinical trial.

To ensure an appropriate evaluation of this association benefit, it will be compared to Ivermectin 1% topical cream alone associated to the placebo of Doxycycline 40 mg MR (CD2475-101).

This clinical trial will compare the efficacy and safety of Ivermectin 1% topical cream associated with Doxycycline 40 mg Modified release (MR) capsules compared to Ivermectin 1% topical cream associated with Placebo in the treatment of severe Rosacea.

Protocol N° RD.03.SPR.113322

version Final dated 10-FEB-2017

Page 41 of 106 CONFIDENTIAL

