2.3 RISK/BENEFIT ASSESSMENT

Rosacea is a chronic, non-life-threatening skin disease characterized by two major features which are a persistent central facial erythema and recurrent eruptions of inflammatory lesions (i.e., papules, pustules, or both).

The two investigational products are marketed individually for rosacea treatment and with proven efficacy and good safety profile including severe rosacea population.

Whatever the randomization arm, all study subjects will benefit from an efficient and safe rosacea treatment.

The association of investigational products is not expected to raise new tolerability issues and has the potential to reach to better and possibly faster efficacy outcome.

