3. CLINICAL TRIAL OBJECTIVES AND CLINICAL HYPOTHESIS

3.1 CLINICAL TRIALS OBJECTIVES

The main objective of this study is to evaluate the efficacy of Ivermectin 1% topical cream associated with Doxycycline 40 mg capsules MR compared with Ivermectin 1% topical cream monotherapy in the treatment of severe rosacea with papulopustular lesions.

The Safety and Patient Reported Outcomes (PRO) will be also evaluated.

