9.1.1.4 Safety variables

- Incidence of adverse events
- Incidence of serious adverse events

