9.1.2.4 Missing values

The last observation carried forward (LOCF) method will be used to impute missing values of Inflammatory Lesion count, CEA, IGA and Stinging/burning sensation. If no post-baseline data

Protocol N° RD.03.SPR.113322

version Final dated 10-FEB-2017

Page 76 of 106 CONFIDENTIAL

are available, baseline will be carried forward. Thus, the number of subjects will not vary at each visit. The other missing values will not be replaced (observed data).

9.1.3 **Data presentation and graphics**

All continuous data will be summarized using usual statistics: number of values, mean, median, standard deviation, minimum and maximum, and by frequency distribution (n, %) for qualitative data. For ordinal data, both frequency distribution and usual statistics will be presented. All tables will be presented by clinical trial treatment and by visit (when applicable).

Therapies that have been stopped before the baseline visit will be presented as prior therapies. Those reported at screening or starting between screening and baseline visits and still continuing after baseline will be classified as concomitant therapies.

The adverse events will be descriptively summarized (n, %) for the safety population (APT). The adverse events will be descriptively summarized (n, %) by relationship to clinical trial treatments within System Organ Class (SOC) and preferred term (MedDRA). Subjects will be descriptively summarized (n, %) by intensity (*i.e.* mild, moderate and severe) of adverse events, SOC and preferred terms. Deaths and serious adverse events will be reported as well as withdrawals due to adverse events. A subject will be counted only once per System Organ Class (SOC) and only once per preferred term even if more than one occurrence of an event was reported within a SOC or preferred term. In the summary by categories of intensity, the adverse event with the highest intensity will be used. The subject will be counted only once per SOC (highest intensity whatever the AE within the SOC) and once per preferred term (highest intensity whatever the AE within the preferred term).

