9.1.4 Statistical analyses

Any changes of the statistical analyses decided after the database lock will be justified and documented.

The definition of the populations will be finalized after a blind data review meeting, during which the distribution of subjects per site will be reviewed. In case of too small sites or in case of severe unbalance between the size of sites, some sites may be combined, e.g. per geographical area, to form analysis-center for purpose of stratification of the statistical analyses.

The primary objective of this study will be to demonstrate the superiority of the Ivermectin 1% topical cream associated with Doxycycline 40 mg MR capsules compared to versus Ivermectin 1% topical cream associated with Placebo, in terms of Inflammatory Lesion count at week 12.

The primary efficacy endpoint will be analyzed by using the Cochran-Mantel-Haenszel (CMH, FREQ procedure from SAS®) statistic, stratified by center (or analysis-center) after ridit

Protocol N° RD.03.SPR.113322

version Final dated 10-FEB-2017

Page 77 of 106 CONFIDENTIAL

transformation with the row mean difference statistics, testing the hypothesis of equality on ITT/LOCF population. PP analysis will also be performed to assess the robustness of the results obtained on ITT/LOCF population. The p-values will have to be inferior to 0.05 at week 12.

The secondary efficacy variables, questionnaires will be analyzed similarly as primary analyses on appropriate population.

The subject characteristics (disposition, previous and concomitant therapies, study treatments duration/ compliance, demographics, baseline characteristics,...), lesion counts and adverse event(s) will only be summarized descriptively, on appropriate population.

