6. STATISTICAL METHODS AND DATA CONSIDERATIONS

SAS version 9.3 will be used for all analyses. All tests will be two-sided and significance will be declared at a 0.05 level.

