6.5.2 Adverse Events

The adverse events will be summarized (n, %) for APT population by parallel group. Deaths and serious adverse events will be reported as well as withdrawals due to adverse events. In case of worsening of rosacea, a specific questionnaire was filled on and the results will be listed.

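### Adverse events are tabulated per arm with no between-arm estimate or interval, so similar percentages alone cannot show that the capsule adds no risk

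*Protocol*

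**What the plan says.** **Aim.** Protocol section 5.2, which discusses the design, states: "This clinical trial will compare the efficacy and safety of Ivermectin 1% topical cream associated with Doxycycline 40 mg Modified release (MR) capsules" against the cream with placebo capsules. The formal objective in protocol 3.1 uses a weaker verb: "The Safety and Patient Reported Outcomes (PRO) will be also evaluated". The synopsis, protocol 9.1 and SAP section 2 match the objective.

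**Safety variable.** Protocol 9.1.1.4 lists "Incidence of adverse events", and the same for serious adverse events.

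**Analysis.** Protocol 9.1.4 says that "lesion counts and adverse event(s) will only be summarized descriptively, on appropriate population". SAP 6.5.2 says: "The adverse events will be summarized (n, %) for APT population by parallel group". Protocol 9.1.3 and SAP 6.1 agree.

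**Output.** SAP Tables 44 to 53 give events and subject n (%) per arm, broken down by relatedness, severity, system organ class and preferred term. There are separate tables or listings for serious events and events leading to discontinuation, and Table 54 lists worsening of rosacea. None of these has a difference, ratio, interval or p-value. The efficacy and patient-reported tables, apart from those marked descriptive, carry a CMH p-value.

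**Prior expectation.** Protocol 2.3 says: "The association of investigational products is not expected to raise new tolerability issues".

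**The concern.** The two arms share the cream and differ only in the capsule (protocol 5.1, SAP 3.1). The between-arm difference in adverse event risk is therefore the randomised estimate of the capsule's added risk on top of ivermectin. Protocol 5.2 says the association has never been assessed in a randomised trial for rosacea, so this difference is new safety information. No planned table reports it or says how precisely it is known.

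The trial was sized on lesion counts. With this sample size, two similar adverse event percentages are compatible with a wide range of true differences. A reader who sees two close columns has no measure of that range, and neither document warns that close percentages are weak evidence of equal risk.

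**Working it through.** **1. The plan's own figure.** Inputs from protocol 9.2 and SAP 3.2: difference 15 points, SD 35, power 90%. Two-sided 0.05 is from SAP section 6 ("All tests will be two-sided and significance will be declared at a 0.05 level").

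n per arm = 2 × (1.960 + 1.282)² × (35/15)² = 2 × 10.507 × 5.444 = 114.4. The plan states 114 (rounding up gives 115), and power at 114 is 0.899. Inflation: 114 / (1 − 0.15) = 134.1, so 135 per arm. The sample size reproduces. Adverse events play no part in it.

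**2. What equal percentages leave open.** The documents give no adverse event rates, so the rates below are assumptions. I take 135 per arm as the maximum, because the safety population drops subjects known never to have used treatment (protocol 9.1.2.3, SAP 5.3).

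Newcombe 95% interval for d = p1 − p2, where (l, u) are the Wilson limits of each arm:
- lower = d − √[(p1 − l1)² + (u2 − p2)²]
- upper = d + √[(u1 − p1)² + (p2 − l2)²]

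Example, 7 of 135 in both arms: p = 5.19%, Wilson limits 2.53% and 10.32%. Upper = √[(10.32 − 5.19)² + (5.19 − 2.53)²] = √(26.3 + 7.1) = 5.8 points.

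| Observed, each arm (n = 135) | Rate | 95% interval for the difference |
|---|---|---|
| 0 v 0 | 0% | ±2.8 points |
| 3 v 3 | 2.2% | ±4.4 |
| 7 v 7 | 5.2% | ±5.8 |
| 14 v 14 | 10.4% | ±7.5 |
| 27 v 27 | 20.0% | ±9.6 |
| 40 v 40 | 29.6% | ±10.8 |
| 54 v 54 | 40.0% | ±11.5 |

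Unequal example: 14 v 7 of 135 gives +5.2 points (−1.4 to +12.0).

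Sensitivity to a smaller safety population, using the plan's 114 per arm: 6 v 6 gives ±6.4, 11 v 11 gives ±8.0 and 23 v 23 gives ±10.4 points.

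**3. Chance of detecting an excess.** This is for scale only; no test is proposed. Two-sided 0.05, 135 per arm, normal approximation:

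power = Φ{[Δ − 1.96 √(2p̄(1 − p̄)/n)] / √[(p1(1 − p1) + p2(1 − p2))/n]}

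For 5% v 10%: (0.05 − 1.96 × 0.0321) / 0.0319 = −0.40, so power is about 34%. For 10% v 15% it is about 24%. The excess detectable with 80% power is about 10 points from a 5% rate, 13 from 10% and 15 from 20%.

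**The case against.** The case for leaving the plan alone is substantial.

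- Section 5.2 is narrative and explains the choice of comparator. The stated objectives say safety will be evaluated, superiority is claimed only for lesion counts, and the descriptive approach to adverse events is stated openly in both documents. A side-by-side table from a randomised trial is itself a comparison. This stands: a reader might infer that the plan contradicts itself or breaks a promise of safety inference, but section 5.2 promises no interval or test.
- A reader might also infer that the sponsor plans to conclude there is no added risk. The documents do not support that. The sentence in protocol 2.3 is a risk/benefit expectation given before the trial, and no safety margin, non-inferiority claim or conclusion of no difference is planned.
- Table 44 gives N and subject n (%), so anyone can compute a difference and an interval. This also stands: the data are available and only the summary is missing.
- Stinging/burning (Table 21) and the satisfaction question on being bothered by side effects (Part A, Table 36) fall under between-arm CMH tests. They bear on tolerability, but neither is an adverse event analysis.
- The event rates are assumed, and the documents set no threshold for an important excess. Hence the range above, and no claim that any one excess matters clinically.

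What survives is narrower. The plan gives no between-arm estimate and no measure of uncertainty for adverse events, and at this sample size the uncertainty is large.

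**Conclusion.** The point holds as a low-severity improvement. Adverse events are summarised per arm only, although the arms differ only in the capsule and section 5.2 speaks of comparing safety. With at most 135 per arm, equal observed rates of about 5%, 10% and 20% leave room for an added risk of about 5.8, 7.5 and 9.6 points, and somewhat more if the safety population is smaller. Similar percentages alone cannot show absence of added risk.

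The result rests on assumed event rates, on 95% Newcombe limits and on subject-level counting. It does not show that the descriptive plan is wrong, or that either document intends to claim equal safety.

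**What to change.** In SAP 6.5.2 and Table 44, add a column with the risk difference (IVM/Doxy minus IVM/Placebo) and its 95% interval, by Newcombe or Miettinen-Nurminen. Apply it to the main subject-level rows: any, related, severe, serious, leading to discontinuation, dermatologic, and worsening of rosacea. Label the column descriptive and give no p-values. Add one sentence that the trial is not sized to exclude an added risk. Record the addition in SAP section 7 as a change from the protocol analysis plan. If the SAP is already final, protocol 9.1 requires the change to be documented in the trial report.

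I would not extend intervals to every system organ class. Counts there will often be sparse, and many unadjusted intervals invite chance signals. Nor would I tie the wording of conclusions to the upper limit, since no margin is defined.

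The cost is one column and two short additions to the SAP. It needs no new data and does not affect the primary error rate. The downside is that the intervals will be wide and unadjusted for multiplicity, and will show how limited the safety evidence is.
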